## Study Protocol and Statistical Analysis Plan

We propose investigation into the efficacy of sleep hygiene interventions on Americans ages 50-80. This will be done by examining the effectiveness of two separate interventions on improving sleep hygiene habits and physiological markers of sleep provided by wearable technology on sleep efficiency, time in bed, time actually sleeping, and time spent at each stage of sleep. The proposed research project will evaluate the efficacy of sleep hygiene education on CDOA and assess the ability of daily automated text messaging in CDOA to serve as an effective augmentation for sleep hygiene education. This research topic corresponds to the South Dakota Biomedical Research Infrastructure Network (BRIN) area of focus: "Physiological (including cellular) and developmental responses to stimuli." Physiological markers of sleep provided by wearable technology on sleep efficiency, time in bed, time actually sleeping, and time spent at each stage of sleep.

### *Research Plan*

#### **Specific Aim 1: Evaluate the efficacy and feasibility of sleep hygiene education on CDOA.**

Rationale: Our first aim is to determine if sleep hygiene education can be beneficial in improving sleep health in the CDOA population. Sleep hygiene education has been shown to be effective in university students, high school students, athletes, and working adults, but up until very recently has yet to be shown in CDOA. Recently, Tucker et al. published a pilot study looking at virtual sleep health education in older adults and found significant changes in sleep quality, maladaptive sleep health behaviors, and daytime sleepiness compared to controls. In this six-week study, six 30-minute videos were used to educate participants on sleep health.[23] A variety of other sleep hygiene education tools have been used to assist in improving sleep health in younger populations, but a one-time educational video was chosen for this project as this was the most popular intervention in previous studies and because we wanted to explore if a one-time educational video would show similar findings as the recent 6-week Tucker et al. study had in regard to sleep health behavior change.[5, 23] Therefore, a 4-week, home-based, technology-supported program targeting sleep hygiene will be conducted among 80 CDOA, ages 50-80 using a 30-minute educational video. Eighty participants is based off of the systematic review performed by Murawski et al. which reviewed sleep health intervention research studies which had participant sizes ranging from 19 to 391 with a median of 84.[5] Taking into account a potential dropout rate of 20%, the initial total number of participants to be recruited will be 100. Similar studies performed in younger populations have shown 4-weeks is an effective time frame to implement sleep hygiene education. This in combination from data from the Murawski review which showed an average study duration of 5-weeks with a mode of 4-weeks, therefore 4-weeks was chosen for our study duration.[5] During the 4-week study, several physiological markers will be taken. These markers will be taken from data collected on the FitBit Inspire HR device and will include sleep efficiency, time in bed, time actually sleeping, sleep midpoint, and time spent at each stage of sleep. FitBit was the device chosen to track these markers due to its efficacy and comparability to the Actigraph device along with FitBit's usability.[32] Of the several wearable devices that track sleep on the market, FitBit is used in more biomedical clinical research than any other consumer wearable.[33] The FitBit Inspire HR 2 was specifically chosen given its ability to track sleep along with it aligning most closely with

the FitBit Alta (now out of stock with FitBit) that was proven comparable and slightly more accurate to actigraphy as researched by Chinoy et al. in 2020.[30]

Experimental design: The proposed 3-year pilot study will begin in the fall (September 2022) and conclude before the end of the academic year (May 2025). This proposal design outlines the first year of this 3-year study. The first step in the experimental process will be the creation of a 30-minute sleep hygiene education video that will be provided to participants to watch on either a smartphone or computer. The video will be created by the PI and student researcher(s) and reviewed and modified based on feedback from the mentors. This video will include tips to improve sleep hygiene and habits. The video will provide education on the value of having a consistent time of going to sleep and waking up in the morning, setting the bedroom up so that it is a comfortable temperature, dark, quiet, and relaxing. The video will also include information regarding the value of removing electronic devices from the bedroom, the importance of exercise, along with avoiding caffeine, alcohol and large amounts of food prior to going to bed.[34] The principal investigator and student researcher(s) will recruit participants through flyers and word of mouth. Flyers will be placed at senior centers, community centers, and medical centers in Rapid City, SD. Interested participants will email or call [name] to enroll in the study. [name] will meet with the participant to determine eligibility status for the study. Due to the use of human subjects in this study, the research protocol will be approved by the University of South Dakota, Black Hills State University institutional review boards, and the National Institutes of Health prior to participant recruitment. Participant inclusion criteria will include participants ages 50-80, own a smartphone with the capability of receiving text messages. Exclusion criteria: a diagnosed sleep disorder such as insomnia or obstructive sleep apnea, and inability to wear any sleep tracking device on their wrist. During the initial visit, participants will read through and sign informed consent explaining the procedures and expectations of them during the study. The participants will then complete the following questionnaires related to the primary objectives of the study: the Ru-SATED questionnaire which includes the Sleep diary (based on the Consensus Sleep Diary) and Epworth Sleepiness Scale, Pittsburgh Sleep Quality Index, and the Sleep Hygiene Index. Participants will also complete the Perceived Stress Scale, Numeric Pain Rating Scale, and Patient Specific Functional Scale as secondary outcomes. Initial data collection will consist of taking anthropometric measurements and vital signs (Figure 1), with the assistance of the student researcher. The anthropometric measurements will include the following: body weight, height, and body mass index (BMI). BMI will be calculated by the standard method (body weight [kg]/height [m]) from weight and height measurements. The vital signs assessed will be resting blood pressure, heart rate, and respiratory rate. Following anthropometric data collection and vital signs, the participants will be instructed on the use of the wearable sleep tracker and provided assistance with setting up and charging the device. Participants will be instructed to contact the PI with any questions throughout the study by email or phone. The participants will then watch the sleep hygiene education video created by the research team.

Following the initial meeting with the PI, the participants will wear the sleep tracker on their wrist during the day and night for 4 weeks. The sleep tracker will monitor the physiological markers of sleep provided by wearable technology on sleep efficiency, time in bed, time actually sleeping, sleep midpoint, and time spent at each stage of sleep. Within the first week of participating in the study, student researcher(s) will contact the participant and perform a short 5- minute qualitative interview on the participants understanding and comprehension of the educational video along with a satisfaction survey (using a 5-point Likert scale). At the end of

the 4-week study period, the PI and/or student researcher(s) will once again meet with each participant. The participant will complete the following questionnaires once again: Sleep diary, Epworth Sleepiness Scale, Pittsburgh Sleep Quality Index, Sleep Hygiene Index, Perceived Stress Scale, Numeric Pain Rating Scale, and Patient Specific Functional Scale. Acceptability will be again assessed using a satisfaction survey (5-point Likert scale) and qualitative interview. Anthropometric data collection and vital signs will be reassessed, and the sleep tracker will be returned to the PI. Pre/post measurements will be compared and data analyses will be conducted using a 2x2 mixed factorial repeated measures ANOVA test. The PI will be assisted in the stats process by her mentor, [name] along with her peer in the psychology department at her university.

[figure not shown]
During the first year of this study, when in the treatment development phase, our primary outcomes for feasibility will be the following: recruitment (people enrolled from people contacted), retention and attrition (participants who complete the study and number who drop out), adherence (number of sessions attended and adherence to intervention protocol). Acceptability will be assessed using the satisfaction survey (5-point Likert scale) and qualitative interview. This information will be used to tailor the intervention to CDOA to further assess treatment effect in year two and three.

Assessing overall sleep health is relatively new and therefore there is no established gold standard, however the Ru-SATED questionnaire (Table 1) has been shown to be a reliable and valid measure of sleep health.[35] We will use this in combination of objective data from the FitBit device to measure sleep health. Each sleep health domain will be dichotomized using the cut-off points in Table 1 with 0 = poor sleep health and 1 = good sleep health. The domains will be summed to create the composite sleep health score ranging from 0 - 6 with a higher score indicating better sleep health.

Sleep health domain	Source	Operational definition	Cut-off for good sleep health
Regularity	FitBit	Standard deviation of sleep midpoint, which is calculated as [sleep onset + (wake time – sleep onset/2)]	<60 min
Satisfaction	Sleep Diary	The sleep diary includes an item to rate “restedness upon awakening” with 0 = “not at all”, 1 = “somewhat”, 2= “moderately”, 3 = “quite a bit”, and 4 = “extremely”. Satisfaction will be operationalized as the average “restedness” score	Average of ≥3
Alertness	Epworth Sleepiness Scale	Epworth Sleepiness Scale which consists of 8-items of various activities (ie. sitting and reading, watching TV, etc) answered using a 4-point Likert Scale with 0 = “would never nod off” to 3 = “high chance of nodding off”	≤10
Timing	FitBit	Average sleep midpoint	2am-4am

Efficiency	FitBit	Average total minutes of sleep divided by time in bed multiplied by 100	>85%
Duration	FitBit	Average total minutes of sleep	6-8 hours

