**Figure 1: Study design for Specific Aim 1.**

**Specific Aim 2: Assess the ability of daily automated text messaging in CDOA to serve as an effective augmentation for sleep hygiene education.**

Rationale: Our second aim is to study the effectiveness of sending automated text messaging as an effective augmentation for sleep hygiene education in CDOA. With the promising short term results of a one-time sleep hygiene education session in young adults and the working adult population, we want to test if reinforcing the education daily through the use of a simple text message over the course of 4 weeks provides even greater and more sustainable results on changing people’s sleep behaviors. The expansion of smartphone technology combined with the abundance of services offering bulk messages to be sent out automatically provides an opportunity to reinforce the initial education with continual reminders of good sleep habits that an individual can practice over the course of 4-weeks. Given that 86% of adults over 50 now consistently use text messaging; it is safe to say this is an easy way to provide daily education and reminders on good sleep habits to this population.[28] If a new habit can be solidified during this timeframe, perhaps we will see long-term changes in sleep that will greatly improve overall health and wellness. For these reasons, we want to explore using automated text messaging as a supplement to our 30-minute educational video for sleep hygiene education.

Experimental design: Following anthropometric data collection and vital signs, as well as having the participants watch the sleep hygiene education video created by the research team, the participants will be randomly assigned to one of two groups (Figure 2). The intervention group will receive daily automated text messages scheduled for 8:00 pm every evening. The text messages will include a variety of sleep hygiene behavioral tips for the participant to try (Table 2). The participants will receive the text messages for a total of 4 weeks. The control group will not receive any intervention during this time frame. Following the 4 weeks, PI and student researcher(s) will meet again with the participants to collect the same data that was collected at the initial visit. Each participant will have a total of 2 sessions to complete with each session taking approximately 45-60 minutes to complete.

Sleep Hygiene Education Video Group

(n=15)

Sleep Hygiene Education Video Plus Daily  

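### The planned sample size is not reconciled: 80 participants (100 recruited) under Specific Aim 1, but two arms of 15 in the Figure 2 labels, with no visible text linking them

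*Combined protocol and SAP*

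**What the plan says.** All references are to the combined protocol and SAP.

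- **Specific Aim 1, Rationale.** The programme is a "technology-supported program targeting sleep hygiene will be conducted among 80 CDOA, ages 50-80 using a 30-minute educational video". The number is set by reference to a systematic review of sleep health interventions (sizes 19 to 391, median 84), with no power calculation. The text continues: "Taking into account a potential dropout rate of 20%, the initial total number of participants to be recruited will be 100".
- **Specific Aim 1, Experimental design.** On scope: "This proposal design outlines the first year of this 3-year study". On analysis: "data analyses will be conducted using a 2x2 mixed factorial repeated measures ANOVA test".
- **Specific Aim 1, feasibility outcomes.** "During the first year of this study, when in the treatment development phase, our primary outcomes for feasibility will be the following". The list includes "retention and attrition (participants who complete the study and number who drop out". For later years: "This information will be used to tailor the intervention to CDOA to further assess treatment effect in year two and three".
- **Specific Aim 2, Experimental design.** After baseline measurements and the video, "the participants will be randomly assigned to one of two groups (Figure 2". No subset, second cohort, separate recruitment or separate sample size is described.
- **Specific Aim 2, Figure 2 labels.** The video group and the video-plus-text group are each labelled n=15.

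**The concern.** Aim 2 appears to randomise the same people whom Aim 1 recruits. Its participants have had the same measurements and watched the same video, and the text names no narrower group. The 2x2 analysis described under Aim 1 needs two groups, and the only two groups in the document are the Aim 2 arms. One would therefore expect the arm sizes to add up to 80 or 100. They add up to 30.

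Two things depend on which number holds:

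- **The randomised comparison.** Video against video plus text is the only randomised question, and its precision depends on the number per arm.
- **First-year feasibility.** Retention is a first-year primary feasibility outcome, and its precision depends on how many people are enrolled that year.

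Without one reconciled set of numbers, a final enrolment of 30, 80 or 100 could each be reported as the planned size.

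**Working it through.** **1. Reproduce the plan's own figure.** Inputs from the Aim 1 rationale: 80 participants, 20% dropout.

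80/(1 − 0.20) = 100. This matches the stated recruitment number, so the rationale is internally consistent. It also implies that 80 is the number remaining after dropout.

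**2. Compare with the Figure 2 labels.** 15 + 15 = 30. Then 30/80 = 37.5% and 30/100 = 30%.

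**3. Does dropout bridge the gap?** The labels do not say whether 15 means randomised or completing, so both are tried.

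- Completing: 30/0.80 = 37.5, so 38 recruited.
- Randomised: 30 × 0.80 = 24 completing.

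Neither reaches 80 or 100.

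**4. Does staging over three years bridge it?** Three equal cohorts of 30 give 90 recruited and 90 × 0.80 = 72 remaining, which does not match. Unequal cohorts can be made to match (30 + 70 = 100 recruited; 24 + 56 = 80 remaining), but the 70 is found only by subtraction. Nothing says that cohorts are equal and nothing gives a number by year, so this step neither confirms nor excludes staging.

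**5. Illustration for the randomised comparison.** The documents give no alpha, power, SD or pre/post correlation. Assumed: two-sided 5%, 80% power, equal arms, equal pre and post SD.

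The group-by-time F in a 2x2 mixed ANOVA equals the squared t statistic on change scores. The detectable difference in raw SD units is therefore d × √(2(1 − ρ)), with d taken from the noncentral t distribution. At ρ = 0.5 the multiplier is 1.

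| Completing per arm | How it arises | ρ = 0.3 | ρ = 0.5 | ρ = 0.7 |
|---|---|---|---|---|
| 12 | 15 randomised, 15 × 0.80 | 1.42 | 1.20 | 0.93 |
| 15 | 15 completing | 1.25 | 1.06 | 0.82 |
| 40 | 80/2 | 0.75 | 0.63 | 0.49 |

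The multiplier cancels in the ratios, so they do not depend on ρ, but they do depend on what 15 means:

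- 15 completing against 40 completing: 1.060/0.634 = 1.67.
- 12 completing against 40 completing: 1.197/0.634 = 1.89.

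**6. Illustration for first-year retention.** Exact (Clopper-Pearson) 95% intervals at about the plan's own 80% retention:

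| Enrolled in year 1 | How it arises | Retained | 95% interval |
|---|---|---|---|
| 30 | 15 means randomised | 24/30 = 80% | 61% to 92% |
| 38 | 15 means completing | 30/38 = 79% | 63% to 90% |
| 100 | the Aim 1 recruitment number | 80/100 = 80% | 71% to 87% |

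**The case against.** The strongest defence is that the two numbers describe different things. The 80 and 100 stand under Aim 1 and the two 15s under Aim 2. The document calls itself a pilot, says that it outlines year one of three, and treats that year as treatment development. A first-year randomised stage of 30 within a larger total fits that structure. So would an Aim 2 subset of 30, with 80 kept for the Aim 1 pre/post question. The Figure 2 drawing is not shown, so a scope note inside it cannot be excluded.

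Much of this stands: the difference is unexplained, and neither number is proved wrong. It does not remove the conflict, because no visible text states a stage or a subset or gives any number by year or by aim. The scope sentence also cuts the other way: if the design described is year one, the 100 could be year-one recruitment. The n=15 labels survive as text, so the gap does not come from the missing drawing.

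It is also fair to object that the consequences are limited. The study is a pilot with first-year feasibility outcomes, and every power input above is assumed. That bears on how much weight the illustrations deserve. It does not bear on whether the planned number should be clear.

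**Conclusion.** The sample size is inconsistent as written. The only randomised comparison carries 30 participants in its labels, against 80 participants and 100 recruited in the rationale, and no visible text connects them or says whether 15 means randomised or completing. That finding rests on the visible text alone.

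The size of the consequence is illustrative and rests on the assumptions in the working. At a correlation of 0.5, the detectable difference is larger than the 0.63 SD for 40 per arm by a factor of 1.67 if 15 means completing, or 1.89 if it means randomised. The retention interval is about 27 points wide (90 − 63) with 38 enrolled or 31 points (92 − 61) with 30, against 16 points (87 − 71) with 100.

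A reader might infer two stronger conclusions that the documents do not support:

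- **That the trial will really randomise only 30, or that the 80 is an error.** The documents do not show which number is wrong.
- **That the trial falls short of its planned power.** No power is stated. The 80 comes from the sizes of earlier studies, so there is no stated power to lose.

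**What to change.** State the number randomised and the number expected to complete, per arm, per aim and per year, and make the Aim 1 rationale and the Figure 2 labels agree. The wording depends on what the sponsor intends:

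- **80/100 applies to the randomised comparison:** correct the labels to about 50 recruited (100/2) and 40 completing (80/2) per arm, if allocation is equal.
- **30 is the whole study:** restate the rationale as 30, and say whether that means randomised or completing.
- **30 is year one only:** say so, and give later-year numbers that sum to the total.
- **30 is an Aim 2 subset:** keep 80/100 for Aim 1, state that only 30 are randomised, and say how they are selected.

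The cost is a correction to text and figure labels, with no added participants. The downside is that the stated size for the randomised comparison becomes less favourable if 30 is the real number. If 80/100 applies but resources were set for 15 per arm, the sponsor would need to confirm them; the documents do not say.

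### FitBit wear starts only after the video, so the FitBit markers and the 0-6 sleep health composite have no pre-video value, and Aim 1's efficacy question cannot be answered on them

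*Combined protocol and SAP*

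**What the plan says.** The stated purpose of Aim 1 (Rationale) is: "Our first aim is to determine if sleep hygiene education can be beneficial in improving sleep health in the CDOA population". The opening paragraph of the document also names wearable markers of sleep as a target of both interventions.

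The order of events is set out under Specific Aim 1, Experimental design. At one initial visit participants complete questionnaires, have measurements taken and are helped to set up the tracker. Then: "The participants will then watch the sleep hygiene education video created by the research team". The next step reads: "Following the initial meeting with the PI, the participants will wear the sleep tracker on their wrist", for 4 weeks.

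The initial-visit instruments include "questionnaires related to the primary objectives of the study: the Ru-SATED questionnaire which includes the Sleep diary". On how sleep health is measured, the plan says of Ru-SATED: "We will use this in combination of objective data from the FitBit device to measure sleep health". Each domain is dichotomised by Table 1, and "The domains will be summed to create the composite sleep health score ranging from 0 - 6".

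Under Specific Aim 2, Experimental design, assignment follows the video: after "having the participants watch the sleep hygiene education video created by the research team, the participants will be randomly assigned" to video alone or video plus daily texts.

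The only analysis statement is: "Pre/post measurements will be compared and data analyses will be conducted using a 2x2 mixed factorial repeated measures ANOVA test". It does not name the variables it covers.

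**The concern.** A change attributed to the video needs either measurements before the video or a group that does not see it. For the FitBit outcomes the plan has neither. The composite is the plan's own measure of the sleep health that Aim 1 sets out to improve, and it draws most of its domains from FitBit, so it has no baseline either.

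The efficacy part of Aim 1 is what is at stake for this family of outcomes. More participants or a different model would not help, because every recorded night falls on the same side of the video. The missing nights cannot be recovered once the video has been seen.

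The analysis statement raises a second, conditional problem. If the pre/post ANOVA is meant to include the FitBit markers and the composite, no data exist for its pre-video cells. If it covers only measures taken at both visits, the FitBit markers and the composite have no stated analysis.

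**Working it through.** **The plan's own figure.** Recruitment: 80 / (1 - 0.20) = 100, which matches. The documents give no alpha, power, effect size or SD, so there is no power figure to reproduce. The question here is whether the effect can be estimated at all.

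**Nights available.** Before the video: 0. After it: 4 x 7 = about 28 per participant, in both arms.

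**Markers affected.** Sleep efficiency, time in bed, time asleep, sleep midpoint and time in each stage: 5 of 5 types.

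**Composite domains by source (Table 1).**

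| Domain | Source | Scorable before the video? |
|---|---|---|
| Regularity | FitBit (SD over nights) | No |
| Timing | FitBit (average) | No |
| Efficiency | FitBit (average) | No |
| Duration | FitBit (average) | No |
| Alertness | Epworth | Yes |
| Satisfaction | Sleep diary (average) | Only if the diary covers several nights; its schedule is not stated |

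Baseline points: 6 - 4 = 2 at most, or 1 if the diary is a single entry. The 0-6 score cannot be formed.

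**Estimability.** Write the FitBit mean as a linear model with five columns: intercept, video, text, time (late against early weeks) and text x time. The cells observed under the plan are:

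- video only, early: (1, 1, 0, 0, 0)
- video only, late: (1, 1, 0, 1, 0)
- video plus text, early: (1, 1, 1, 0, 0)
- video plus text, late: (1, 1, 1, 1, 1)

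The video column equals the intercept column, so the rank is 4 of 5 and the video effect is not estimable. Adding a pre-video row (1, 0, 0, 0, 0) raises the rank to 5 of 5, and a before/after contrast can be estimated. Early against late weeks shows only change after the video. Arm against arm shows only the effect of texting.

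**What a run-in would give.** For the before/after change in the video-only arm, in SD units, the 95% half-width is t(n-1) x sqrt(2(1 - r)/n), where r is the correlation between baseline and final values. The documents give no r. I take 0.5 to 0.7 as an assumption, and 0.3 as a less favourable case.

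| n in the arm | r = 0.3 | r = 0.5 | r = 0.7 |
|---|---|---|---|
| 40 (80 completers split equally, assumed) | 2.023 x sqrt(1.4/40) = 0.38 | 2.023 x sqrt(1.0/40) = 0.32 | 2.023 x sqrt(0.6/40) = 0.25 |
| 15 (as shown for Figure 2) | 2.145 x sqrt(1.4/15) = 0.66 | 2.145 x sqrt(1.0/15) = 0.55 | 2.145 x sqrt(0.6/15) = 0.43 |

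**Aim 2 without a FitBit baseline.** The time-by-group test compares change scores, whose variance is 2(1 - r) times that of a post-only comparison. The post-only variance relative to it is 1/1.4 = 0.71 at r = 0.3, 1/1.0 = 1.00 at r = 0.5 and 1/0.6 = 1.67 at r = 0.7. The missing baseline may therefore cost Aim 2 nothing. This ratio has no bearing on the Aim 1 problem.

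**The case against.** The strongest reply concerns reach. The document describes year one of three, a treatment-development phase whose primary outcomes are recruitment, retention and adherence, with treatment effect to be assessed further in years two and three. The Rationale for Aim 1 also says the one-time video is meant to be compared with an earlier six-week programme on behaviour change. The outcomes it lists for that programme are sleep quality, maladaptive sleep behaviours and sleepiness. The Pittsburgh index, the Sleep Hygiene Index and the Epworth scale are the natural instruments for these, and all three are completed at both visits. This stands, and it keeps the point from being critical. It does not remove it: Aim 1 names efficacy, and the composite is how the plan says it will measure sleep health.

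On the ANOVA, pre/post most naturally means measures taken at both visits, in which case nothing contradicts. A comparison of early with late wear weeks would also fill both time cells. Both readings are fair. The first leaves the FitBit measures without an analysis. The second is not stated, and all of its data are post-video.

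A run-in would not isolate the video either. Secular trend, regression to the mean, and the effects of wearing a tracker or keeping a diary would remain. This stands too: a run-in supplies the missing baseline, not a control group.

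Figure 1 is not available in the text reviewed, so a run-in drawn only there cannot be excluded. It would, however, conflict with the running text.

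**Conclusion.** The concern holds and should be fixed. As the text describes the study, the FitBit markers and the 0-6 composite have no pre-video value and no no-video comparator, so the video's effect on them cannot be estimated, even as an uncontrolled change. The extent is 0 pre-video nights, 5 of 5 marker types and 4 of 6 composite domains.

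This conclusion follows from the order of events and the sources in Table 1, and needs no numerical assumption. Only the half-widths depend on the assumed r and on the arm size. The damage is confined to this outcome family and falls on the treatment-effect question carried into years two and three.

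**What to change.** **Preferred.** Issue the FitBit and a nightly diary at the initial visit, and record about 7 nights before the video, randomisation and first text. Score the baseline and final composites over windows of equal length, for example the last 7 nights for the final one. For the video, use the change in the video-only arm and label it an uncontrolled before/after contrast; in the text arm the change also includes texting. For texting, use the randomised arm-by-time contrast. State which variables enter the 2x2 ANOVA, and state the diary schedule.

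**Cost.** A protocol amendment and one more device-week per person, 5/4 - 1 = 25%. That is 100 x 4 = 400 rising to 100 x 5 = 500 device-weeks for the 100 recruited, or 30 x 4 = 120 rising to 30 x 5 = 150 if 30 are enrolled. Two in-person visits can be kept if the video is released remotely with a viewing check, randomisation is done remotely after the run-in, and the first-week interview is re-timed to follow viewing. Remote viewing changes how the video is delivered and bears on adherence, a year-one primary outcome. Some participants may also drop out during the run-in, and the documents give no figure for that.

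**If no run-in is feasible.** Drop Aim 1 efficacy and pre/post claims for the FitBit markers and the composite. Analyse them only as a randomised between-arm comparison for Aim 2, and limit the pre/post ANOVA to measures collected at both visits. This costs only analysis wording and a narrower claim, and may be enough for year one. The baseline question should still be settled before years two and three.

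### Four-week acceptability is measured only in participants who attend the closing meeting, by the team that made the video, and no exit assessment is planned

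*Combined protocol and SAP*

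**What the plan says.** All of the following is in the combined protocol and SAP.

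- **Week 1 (Specific Aim 1, Experimental design).** Student researchers contact each participant within the first week. They hold a 5-minute interview on how well the video was understood and give a 5-point Likert satisfaction survey.
- **Week 4 (same section).** At the end of the study period "the PI and/or student researcher(s) will once again meet with each participant", and there "Acceptability will be again assessed using a satisfaction survey (5-point Likert scale) and qualitative interview".
- **Who made the video (same section).** The principal investigator and student researchers create it, with feedback from the mentors.
- **Dropout (Specific Aim 1, Rationale).** The programme is planned for 80 people. "Taking into account a potential dropout rate of 20%, the initial total number of participants to be recruited will be 100".
- **Use of the result (Specific Aim 1, feasibility paragraph).** Dropouts are counted under retention and attrition. Acceptability is named separately, and the combined information is to shape the intervention for years two and three.
- **Aim 2 closing visit (Specific Aim 2, Experimental design).** The team meets participants after 4 weeks "to collect the same data that was collected at the initial visit". Figure 2 shows 15 per group.

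The plan describes no survey or interview at withdrawal, no denominator for acceptability and no rule for missing responses. It does not say whether the Likert survey is self-completed or read out by an interviewer.

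**The concern.** Acceptability of a four-week programme is best judged by everyone who started it, and those who gave up are especially informative about what to change. As written, anyone who has left by the closing meeting contributes no four-week response, so the result describes completers only.

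The week-1 survey fills the gap only in part. By then a participant has had at most one of four weeks of day-and-night tracker wear and, in the text group, about 7 of 28 evening messages. It cannot show whether four weeks of either was tolerable.

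A separate matter is who asks. Both assessments are obtained by members of the team that made the video, which can invite courteous answers. This does not cause missing responses, but it could add to any optimism that selection creates.

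The tailoring of years two and three is at stake. If dissatisfaction is concentrated among those who leave, the team will know how many left but not what they thought of the video, the tracker or the texts. Those views cannot be recovered later.

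**Working it through.** **1. The plan's own figure.** Inputs from Specific Aim 1, Rationale: 80 participants and dropout d = 0.20. Number to recruit = 80 / (1 - 0.20) = 100, which matches the plan. Followed as written, 100 - 80 = 20 of 100 enrolled would have no four-week acceptability response.

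**2. Formula.** Let pC be the proportion satisfied among completers and pD the proportion among dropouts.
- All-enrolled figure = (1 - d) × pC + d × pD
- Completer-only minus all-enrolled = d × (pC - pD)

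**3. Numbers.** The documents give neither pC nor pD, so both are assumptions. With d = 0.20 and pC = 80%:

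| pD (assumed) | All-enrolled | Completer-only minus all-enrolled |
|---|---|---|
| 0% | 0.8 × 80 + 0.2 × 0 = 64% | +16 points |
| 40% | 64 + 8 = 72% | +8 points |
| 80% | 64 + 16 = 80% | 0 |
| 100% | 64 + 20 = 84% | -4 points |

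The extremes for other assumed completer rates are +14 to -6 points at pC = 70% and +18 to -2 points at pC = 90%.

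**4. The same on the Likert mean.** The plan sets no cut-off for satisfied, so a mean may be reported instead. With an assumed completer mean of 4.0, the difference is 0.20 × (4.0 - 1) = +0.6 if dropouts average 1, and 0.20 × (4.0 - 5) = -0.2 if they average 5.

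**5. At the group size in Figure 2.** With 15 per group, 20% dropout is 3 people, leaving 12. If 10 of the 12 are satisfied (assumed), the completer figure is 10/12 = 83%. The all-enrolled figure could lie between 10/15 = 67% and 13/15 = 87%.

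**6. Coverage by time of leaving.**
- Left before the week-1 contact: no response at all.
- Left between that contact and the closing meeting: one early response and no four-week response.
- Attended the closing meeting: both.

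The documents do not say when dropout is expected, so the split between the first two groups is unknown.

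**The case against.** The strongest reply is that the plan already surveys satisfaction twice and does not hide dropout.

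- **Dropouts do answer, at least in part.** A reader might infer that those who leave are never asked. The documents do not support that: the closing assessment is itself described as a repeat, and anyone who leaves after the week-1 contact has answered once. The stated topic, understanding of the video, belongs to the week-1 interview; the survey is not expressly confined to it. For the video-only group the whole educational intervention has been delivered by then. This stands. The gap is in four-week experience, chiefly of the tracker and texts.
- **Direction is not shown.** A reader might infer that acceptability will be overstated. People may leave for reasons unrelated to satisfaction, in which case the error is near zero, and a small understatement is possible. This also stands.
- **Attrition is reported alongside.** A 20% loss would be visible next to completer satisfaction, and both inform tailoring. This softens the consequence, but a count of dropouts does not say what they found unacceptable.
- **Interviewer effect is uncertain.** The survey's mode is not stated, so courtesy bias is a risk and not an established fact.
- **The text group.** From the Aim 2 wording, a reader might infer that this group is never asked about acceptability, because no satisfaction survey is listed for the initial visit. That reading is weak. The Aim 1 closing meeting covers every participant, and the Aim 2 sentence is most naturally shorthand for repeating the outcome measures.
- **Which count applies.** The 100 sits beside 15 per group in Figure 2, so 20 people may not be the year-one number. The formula depends on the dropout fraction, not on the count.

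**Conclusion.** The point holds in a limited form. Followed as written, four-week acceptability is a completer-only result collected by the team that made the video, with no exit assessment. The week-1 survey reduces the problem without removing it.

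At 20% dropout and an assumed 80% satisfied among completers, the gap from the all-enrolled figure lies between +16 and -4 points. The possible overstatement is therefore four times the possible understatement. That overstatement is likelier rests on a judgement that people who leave tend to be less satisfied than those who stay; the documents give no data on this. No size can be put on the interviewer effect.

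For a development-phase pilot with no acceptability threshold, this does not undermine the study. It is worth correcting before recruitment because the missing responses cannot be collected afterwards.

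**What to change.** 1. Make the satisfaction survey a short self-completed form, sent by text link to every enrolled participant at week 4, or at withdrawal if earlier. Include items on the video, the tracker and, for the text group, the texts.
2. Report response counts out of all enrolled, by arm.
3. Show week-1 satisfaction by later completion status, so that early views of those who left can be compared with those who stayed.
4. Give a bound with non-responders counted as not satisfied, labelled as a sensitivity result only. As a main result it would fold attrition, already an outcome, into acceptability.
5. Keep the interview for qualitative use.
6. State in the Aim 2 text that the closing acceptability assessment applies to both groups.

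**Cost.** Protocol wording and an online form. Participants must already own a smartphone that receives texts, and automated messaging is already planned, so no extra visit is needed. Some who withdraw will not reply, and reported satisfaction may be lower. If the form carries a study code it is not anonymous to the team, so self-completion reduces courtesy bias without eliminating it.
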